2.4.4.1.3 Exploratory analysis

All bleeding episodes (treated or untreated)

The on-treatment and treatment policy efficacy analyses are performed by including all bleeding episodes, regardless of administration of factor concentrates or bypassing agent infusion using the same negative binomial model as used for the primary analysis, which only includes treated bleeding episodes.

Time to first bleeding event

The time to first treated bleeding event in the factor or BPA prophylaxis period is calculated as the number of days between Day -168 and the onset date of the first treated bleeding event during the factor or BPA prophylaxis period. The patient is censored at the earlier of Day -1 if no treated bleeding event has occurred. The time to first treated bleeding event in the fitusiran treatment period is calculated as the number of days between Day 1 and the onset date of the first treated bleeding event during the treatment period. The patient is censored at the earlier of Day 190 if no

treated bleeding event has occurred. The time to first treated bleeding event in the efficacy period is calculated similarly from Day 29 as the start of efficacy period. If a patient does not have bleeding episode data collected after Day 28 due to early study discontinuation, the time to first treated bleeding event in the efficacy period is imputed from Day 1 as in the treatment period.

The time to first treated spontaneous bleeding event is calculated similarly.

For on-treatment analysis, time to first treated bleeding episode will be adjusted by intercurrent events.

The proportion of patients who are bleeding free in fitusiran treatment period and factor or BPA prophylaxis period will be estimated using the Kaplan-Meier method and compared using a Cox proportional hazards (PH) regression model with a robust sandwich covariance matrix to account for the within participant dependence, and the study period as a fixed effect. Plots of cumulative mean functions for the number of treated bleeds in the fitusiran treatment period and factor or BPA prophylaxis period will be provided.

Symptoms related to bleeding

Descriptive statistics are provided for symptoms related to bleeding events by each study period.

2.4.4.1.4 Subgroup analysis

Based on the mechanism of action of fitusiran, there should not be difference in the safety or efficacy of fitusiran between hemophilia A or B, either with or without inhibitors. Nevertheless, the subgroup efficacy analysis based on hemophilia type and inhibitor status will be part of subgroup analyses specified below without formal statistical testing due to exploratory nature of these analyses.

The on-treatment and treatment policy efficacy analyses for the primary endpoint and the secondary endpoints based on bleeding episodes are repeated for the following subgroups:

- Hemophilia type (Type A vs B)
- Number of bleeding episodes prior to screening (≤ 10 vs > 10)
- Age group, years (< 18 , 18-64, ≥ 65)
- Cohort A vs Cohort B

In addition, region- and/or country-specific analyses are performed to support regulatory submission as needed.

Negative binomial regression model will be applied only for subgroups that have at least 3 patients and the model converges. Otherwise, only summary statistics are presented.

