b Fitusiran as prophylaxis treatment and permitted on-demand use of factors or BPAs for treatment of breakthrough bleeding episodes. Patients may continue their routine factor or BPA administration schedule for up to the first 7 days of the onset period. For the United States specific requirements see [Section 11.6.1.1](#).

c Not required at Early Termination Visit for patients who complete assessment at EOT Visit and subsequently Early Terminate.

- d* Patients who discontinue study drug dosing for any reason and agree to complete the remaining assessments through the EOS/ET and AT FU visits and may receive treatment consistent with local standard practice for their disease per Investigator judgement, as applicable. For patients who withdraw from the study early and do not consent to complete remaining assessments through the EOS/ET and AT FU visits, every effort should be made to conduct the assessments performed at the EOS/ET visit.
- e* Patients not enrolling in the extension study will complete AT F/U visits at monthly intervals following final fitusiran dose until AT activity level returns to ~60% (per the central laboratory), or per Investigator discretion in consultation with the study Medical Monitor.
- f* The complete medical history/disease history (ie, including bleeding episode and treatment history over the prior 6 months) to be recorded at Screening.
- g* eDiary training will be completed at the Clinic at Screening (see [Section 7.2.1](#)).
- h* A full physical examination will be performed at Screening only; a directed physical exam will be performed at all other visits (see [Section 7.6.3](#)).
- i* Height will be recorded only at Screening for patients > 18 years old. Height for patients < 18 years old and weight for all patients will be recorded at all checked visits ([Section 7.6.2](#)).
- j* 12-lead ECGs will be performed in triplicate. On Day 1, 12-lead ECGs will be performed predose and 4 hours (± 30 min) postdose (see [Section 7.6.4](#)). The Month 7 12-lead ECG will be performed only in those patients who are performing the ET visit and may be performed in singlicate.
- k* Hepatitis C virus antibody positive patients only. FibroScan where available, otherwise FibroTest and APRI.

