7.1 SCREENING/BASELINE ASSESSMENTS

An informed consent form (ICF) or assent form that has been approved by the appropriate Institutional Review Board (IRB)/Independent Ethics Committee (IEC) must be signed by the patient (or legal guardian) before the Screening procedures are initiated. All patients (or their legal guardians) will be given a copy of the signed and dated ICF and/or assent form.

Patient demographic and medical history will be obtained at Screening. Medical history must include documentation of factor concentrate and/or BPA prescriptions (in the medical or pharmacy record) and documentation of reported number of bleeding episodes over the last 6 months (for inhibitor patients) or 12 months (for non-inhibitor patients). Patients will be screened to ensure that they meet all of the inclusion criteria and none of the exclusion criteria. Rescreening of patients is permitted with consultation of the study Medical Monitor.

To complement medical records, information regarding health resource use will be collected as specified in the Schedule of Assessments ([Table 1](#)), including days missed from work/school (as appropriate) and days not able to perform normal activities outside of work/school due to hemophilia, physician office visits, hemophilia treatment site visits, emergency room visits (reason and number), hospitalizations (reason, dates of hospitalization and associated length of stay).

For the United States specific requirements, see [Section 11.6.1.2](#).

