2 STATISTICAL AND ANALYTICAL PROCEDURES

2.1 ANALYSIS ENDPOINTS

2.1.1 Demographic and baseline characteristics

Demographic characteristics

Demographic variables are:

- Age in years (quantitative and qualitative variable: ≥ 12 to < 18 , ≥ 18 to < 65 and ≥ 65 years)
- Sex (Male)
- Race (American Indian or Alaska Native, Asian, Black or African American, Native Hawaiian or Other Pacific Islander, White, Other)
- Ethnicity (Hispanic or Latino, not Hispanic or Latino, not available/not reported)
- Weight in kg
- Height in cm
- Body Mass Index (BMI) in kg/m^2
- Geographic Region (Defined in [Section 2.5.6](#))

Medical or surgical history

Medical (or surgical) history includes all the relevant medical (or surgical) history during the lifetime of the patient.

This information will be coded using the version of Medical Dictionary for Regulatory Activities (MedDRA) currently in effect at Sanofi at the time of database lock.

Disease characteristics

The following disease characteristics are summarized

- Hemophilia type
- Inhibitor status
- Number of bleeding episodes prior to screening (ie, number of bleeds reported in the last 6 months prior to screening for Cohort A and number of bleeds reported in the last 12 months prior to screening for Cohort B)
- Age at diagnosis
- Time from diagnosis to screening

Any technical details related to computation, dates, and imputation for missing dates are described in [Section 2.5](#).

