2.4 STATISTICAL METHODS

All the below statistical analyses are done for Cohort A and Cohort B separately. A pooled analysis is performed after all patients in the 2 cohorts have either finished the Month 7 visit during the fitusiran treatment period or discontinued from the study. Participants treated with fitusiran of 80mg QM and participants treated with fitusiran of 50mg Q2M will be analyzed separately. All the analysis will mainly focus on the participants treated with fitusiran of 80mg QM. The key efficacy, pharmacodynamic and safety data from participants treated with fitusiran of 50mg Q2M will mainly be listed due to the small sample size (only 2 participants). When safety analysis are mentioned in this doc, it refers to SAS1 and/or SAS 2 in this SAP.

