Appendix A Summary of statistical analyses

Efficacy Analyses

Endpoint	Analysis population	Primary analysis	Supportive analysis	Subgroup analysis	Other analyses
Primary endpoint					
Annualized bleeding rate (ABR) in the fitusiran efficacy period (fitusiran treatment period for US protocol) and the factor/BPA prophylaxis period.	EAS 1	Repeated measures negative binomial regression model with On-Treatment Strategy	Yes. Repeated measures negative binomial regression model with Treatment Policy Strategy	Yes. Subgroups are hemophilia type, number of bleeding episodes during the 6 months prior to study, age group, Cohort A vs B, region- and/or country-	Per-protocol analysis Exploratory analysis Zero-inflated negative binomial model Bayesian analysis MI for treatment policy strategy
Secondary endpoints					
Annualized spontaneous bleeding rate in the fitusiran efficacy period and the factor/BPA prophylaxis period	EAS 1	Repeated measures negative binomial regression model with On-Treatment Strategy	Yes. Repeated measures negative binomial regression model with Treatment Policy Strategy	Subgroup analysis will be performed if deemed necessary	No
Annualized joint bleeding rate in the fitusiran efficacy period and the factor/BPA prophylaxis period	EAS 1	Repeated measures negative binomial regression model with On-Treatment Strategy	Yes. Repeated measures negative binomial regression model with Treatment Policy Strategy	Subgroup analysis will be performed if deemed necessary	No
Change in Haem-A-QOL physical health score and total score in the fitusiran treatment period	EAS 1	Descriptive statistics and Mixed Model with repeated measures (MMRM)	Non-parametric Wilcoxon signed-rank test	Subgroup analysis will be performed if deemed necessary	No
ABR in the onset period	EAS 1	negative binomial regression model with On-Treatment Strategy	Yes. negative binomial regression model with Treatment Policy Strategy	Subgroup analysis will be performed if deemed necessary	No

Endpoint	Analysis population	Primary analysis	Supportive analysis	Subgroup analysis	Other analyses
ABR in the treatment period (ABR in the efficacy period for US protocol)	EAS 1	negative binomial regression model with On-Treatment Strategy	Yes. negative binomial regression model with Treatment Policy Strategy	Subgroup analysis will be performed if deemed necessary	No
Annualized weight-adjusted consumption of factor/BPA	EAS 1	Descriptive statistics		Subgroup analysis will be performed if deemed necessary	

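### The prior-bleed subgroup puts one raw cut of 10 on a 6-month count in Cohort A and a 12-month count in Cohort B, so its strata mean different bleeding rates once the cohorts are pooled

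*SAP*

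**What the plan says.** - **The cut.** SAP 2.4.4.1.4 repeats the on-treatment and treatment-policy analyses of the primary endpoint and the bleeding-based secondary endpoints by "Number of bleeding episodes prior to screening (≤ 10 vs > 10". Nothing there annualizes the count. The subgroup analyses are described as exploratory and carry no formal test.
- **The variable.** SAP 2.1.1 defines it as the "number of bleeds reported in the last 6 months prior to screening for Cohort A" and the "number of bleeds reported in the last 12 months prior to screening for Cohort B".
- **The summary table.** The primary-endpoint row of SAP Appendix A names the subgroup as "number of bleeding episodes during the 6 months prior to study", with no split by cohort.
- **Pooling.** SAP 2.4 runs the analyses by cohort and adds: "A pooled analysis is performed after all patients in the 2 cohorts" have finished Month 7 or discontinued. The same subgroup list contains Cohort A vs Cohort B.
- **Data collection.** Protocol 7.1 asks for "documentation of reported number of bleeding episodes over the last 6 months (for inhibitor patients) or 12 months (for non-inhibitor patients". Protocol Table 1, footnote f, describes the history recorded at Screening as "including bleeding episode and treatment history over the prior 6 months", with no longer window for non-inhibitor patients.

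**The concern.** A raw count is a fair measure of bleeding severity only if everyone is observed for the same time. Here one cohort is observed for twice as long as the other, and both are judged against the same number. Within a cohort this does no harm, because the cut always means the same rate. In the pooled analysis neither stratum has a single meaning.

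A reader of the pooled tables would take the two strata as milder and more severe prior bleeders on one scale. Part of the split would instead reflect cohort membership and length of look-back. The same strata would appear in tables for several endpoints under two estimand strategies. In addition, a programmer working from 2.1.1 and one working from Appendix A would build different variables for Cohort B.

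**Working it through.** The documents give no figure for this point, so there is nothing of the plan's own to reproduce.

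**Step 1. Annualize the cut.** Annual rate = count × 12 / window in months.
- Cohort A: 10 × 12/6 = 20 per year.
- Cohort B: 10 × 12/12 = 10 per year.

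**Step 2. Compare the classifications.**

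| Observed annual rate | Cohort A (6-month count) | Cohort B (12-month count) |
|---|---|---|
| 10 | 5: low | 10: low |
| 12 | 6: low | 12: high |
| 16 | 8: low | 16: high |
| 20 | 10: low | 20: high |
| 22 | 11: high | 22: high |

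The discordant band is above 10 and up to 20 per year: 6 to 10 bleeds in 6 months in Cohort A, and 11 to 20 bleeds in 12 months in Cohort B. This step needs no assumption.

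**Step 3. Estimate how many patients fall in the band.** The documents give no distribution of pre-screening bleeds. I therefore assume that it resembles the planning prophylaxis-period ABRs in Protocol 8.1, Tables 9 and 10 (mean/SD 16/14 or 12/11 for Cohort A; 4/5 or 6/7 for Cohort B). Patient rates are taken as gamma with shape k = (mean/SD)², and counts as Poisson over the 2.1.1 window. Counts are then negative binomial with mean m × t, where t = 0.5 or 1 year. The conditional column divides by the probability of meeting inclusion criterion I 03 (at least 2 bleeds in 6 months in A, at least 1 in 12 months in B). N is 26 for Cohort A (30 less up to 4 direct-start patients, who are outside the efficacy set) and 50 for Cohort B.

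| Cohort, ABR mean/SD | k | Mean count | P(band) | P(meets I 03) | P(band, given I 03) | Patients in band |
|---|---|---|---|---|---|---|
| A, 16/14 | 1.31 | 8 | 0.250 | 0.837 | 0.299 | 7.8 of 26 |
| A, 12/11 | 1.19 | 6 | 0.231 | 0.766 | 0.302 | 7.8 of 26 |
| B, 4/5 | 0.64 | 4 | 0.084 | 0.719 | 0.117 | 5.9 of 50 |
| B, 6/7 | 0.73 | 6 | 0.136 | 0.804 | 0.170 | 8.5 of 50 |

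Reading the planning SD as that of an observed 12-month or 162-day ABR, rather than of the underlying rate, gives conditional values of 0.306 to 0.320 in A and 0.096 to 0.169 in B. The picture does not change.

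**Step 4. Size of the high stratum under each rule** (given I 03, same N).

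| Rule | Cohort A | Cohort B |
|---|---|---|
| As written | 6.1 to 8.6 | 7.2 to 11.8 |
| More than 10 per year in both | 13.9 to 16.4 | 7.2 to 11.8 |
| More than 20 per year in both | 6.1 to 8.6 | 1.4 to 3.3 |

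A common cut of 10 per year moves only Cohort A patients, from low to high. A common cut of 20 per year moves only Cohort B patients, from high to low.

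**The case against.** The strongest reply is that little depends on this. The subgroup is exploratory and untested, no decision rule uses it, and prior bleeds is not a covariate in the primary model. Each stratum's rate ratio is a within-patient comparison, so mixed windows change the label of a stratum and not the validity of its estimate. All of that stands, and it limits the weight of the point.

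Second, SAP 2.4.4.1.4 does not itself say that this subgroup is run on pooled data. That is true: pooled use is an inference. It follows from the pooled analysis promised in SAP 2.4, from the Cohort A vs Cohort B subgroup in the same list, which makes sense only on pooled data, and from the absence of any text exempting the prior-bleed subgroup.

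Third, the cohort-specific windows are deliberate and match inclusion criterion I 03 and Protocol 7.1. Agreed: what is missing is the annualization. It is also fair that the two faults are alternatives. If Appendix A's 6-month window governed, the cut would mean one rate in both cohorts. But both texts are current and only one can be followed.

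Fourth, the small Cohort B high stratum at 20 per year matters only within that cohort. Pooled, the high stratum would still hold about 7 to 12 patients (6.1 + 1.4 to 8.6 + 3.3). That is correct, but the by-cohort subgroup analyses would use the same cut, so the caution remains relevant.

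**Conclusion.** The concern holds. As written, the rule classifies the same observed bleeding rate differently by cohort, with cut-points a factor of two apart, and Appendix A contradicts the definition in SAP 2.1.1. The estimate of about 30% of Cohort A and 12% to 17% of Cohort B in the discordant band is illustrative. It assumes that pre-screening bleeding resembles the planning ABRs, that counts are gamma-Poisson, and that all four direct-start places are filled. The misclassification itself rests on none of these.

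The reach is narrow: the pooled exploratory subgroup tables. The primary result is untouched, and neither the by-cohort subgroup analyses nor the US analysis (Cohort A only) is affected by the mixing. It should be corrected because it is a stated rule that gives the wrong grouping when followed, not a missing detail.

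**What to change.** - In SAP 2.4.4.1.4, define the subgroup on the annualized prior bleeding rate: 6-month count × 2 in Cohort A, 12-month count in Cohort B.
- Fix one cut-off before database lock, for example 10 or fewer vs more than 10 per year. A cut of 20 per year is possible but would leave only about 1 to 3 Cohort B patients in the high stratum, around the SAP's own minimum of 3 patients for fitting the model.
- Bring SAP 2.1.1, 2.4.4.1.4 and Appendix A to the same wording.
- Confirm which look-back was actually recorded for Cohort B, since Protocol 7.1 and Table 1 footnote f differ.
- Report the pooled result beside the by-cohort results. A common scale gives the strata one meaning but does not remove their association with cohort: at 10 per year the high stratum would hold about 14 to 16 Cohort A and 7 to 12 Cohort B patients.

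The cost is wording in three places and a one-line derivation, provided the 12-month count was recorded for Cohort B as Protocol 7.1 requires. No new data are needed in that case.

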2.4.4.2 Analyses of secondary efficacy endpoints

2.4.4.2.1 ABR in the fitusiran efficacy period (Key secondary endpoint for US protocol)

Analysis includes all bleeding episodes occurring in the fitusiran efficacy period. The on-treatment and treatment policy efficacy analysis are repeated with this endpoint. Estimated mean ABR and its 95% CI will be presented. No formal hypothesis testing will be performed.

2.4.4.2.2 Annualized spontaneous bleeding rate in the fitusiran efficacy period and the factor/BPA prophylaxis period

Analysis includes spontaneous bleeding episodes occurring in the factor/BPA prophylaxis period and the fitusiran efficacy period. The on-treatment and treatment policy efficacy analyses are repeated with this endpoint.

2.4.4.2.3 Annualized joint bleeding rate in the fitusiran efficacy period and the factor/BPA prophylaxis period

Analysis includes joint bleeding episodes occurring in the factor/BPA prophylaxis period and the fitusiran efficacy period. The on-treatment and treatment policy efficacy analyses are repeated with this endpoint.

2.4.4.2.4 Change in Haem-A-QOL physical health score and total score in the fitusiran treatment period and the factor or BPA prophylaxis period

Change from baseline in Haem-A-QOL physical health score and total score (in patients ≥ 17 years of age) in the factor or BPA prophylaxis period and fitusiran treatment period are analyzed using a mixed model for repeated measure analysis (MMRM) with robust sandwich covariance matrix, with fixed effects of study period (factor or BPA prophylaxis period and fitusiran treatment period), baseline Haem-A-QoL physical health score and total score for each study period as covariates. Least square means of the physical health score and total score in each treatment period and the difference of the least square means of the physical health score and total score in the two periods (along with the 95% CI and p-value) are presented. The normality assumption based on MMRM model is examined and a sensitivity analysis based on the non-parametric Wilcoxon signed-rank test is performed. For patient with missing assessment due to early withdrawal, a sensitivity analysis is performed by imputing the domain score and total score as the worst score if the reason of withdrawal is treatment-related in the fitusiran treatment period, and as the average score for other reasons of withdrawal that are not treatment related in the fitusiran treatment period. The same analysis as main will be performed as a sensitivity analysis by excluding values of those who completed Haem-A-QoL at baseline after first dose of fitusiran.

To evaluate the impact of Covid-19, the same MMRM model will also be repeated on Covid-19 unaffected set. In addition, a sensitivity analysis using same MMRM model will be performed excluding the data impacted by Covid-19 major/critical protocol deviation. A supportive analysis will be repeated on the patients whose responses level to EQ-5D dimensions “anxiety/depression” is no change or improved from baseline of factor or BPA prophylaxis period.

Change from baseline in Haem-A-QoL physical health score and total score in the factor or BPA prophylaxis period and fitusiran treatment period are also summarized descriptively by study period.

Domain scores, standardized scale scores, and transformed scale scores for Haem-A-QoL and their changes from baseline in the factor or BPA prophylaxis period and fitusiran treatment period are summarized by study period.

To evaluate the association between the change in Haem-A-QoL and other clinical measures, the analysis of change from baseline in the Haem-A-QoL physical health score and total score are stratified by ABR level (0, 1-5, >5) and concomitant pain medication use (Y, N). The ABR level is based on on-treatment strategy during the fitusiran treatment period and factor or BPA prophylaxis period.

The summary of adherence with Haem-A-QoL measurement is also provided.

